2. To evaluate the effect of NSS on clinical and biochemical changes among patients.
3. To evaluate the effect of NSS on the biochemical status associated with overall mortality.

Study hypotheses

The null hypothesis: The nutritional support system will not reduce mortality or increase survival in patients with COVID-19 in stage III and comorbidities compared to conventional nutritional therapy.

Research hypothesis: The nutritional support system will reduce mortality and increase survival in patients with COVID-19 in stage III and comorbidities compared to conventional nutritional treatment.

Section 3: Trial Methods

9. Trial design - description of trial design

Item 9: Brief description of trial design including type of trial

Randomized, blinded, controlled clinical trial. Selected patients will be randomized into two groups: 1) Control Group (CG) will receive the hospital diet and 2) Intervention Group (IG) will receive the hospital diet and the NSS. Treatment allocation will have a 1:1 ratio.

10. Randomization

Randomization will be performed using a raffle; eighty numbers are to be placed (from 1 to 80). Subsequently, each number will be randomly selected from the raffle and sequentially assigned to one of the two groups, until reaching 40 numbers per group. Each number represents the moment the patient enrolls. In this way, once the recruitment starts, the first patient will be assigned number one; the second will be number two, and so on.

11. Sample size

Item 11: Full details of the same size calculation or alternatively reference to sample size calculation in protocol (instead of replication in SAP).

The sample size will be calculated using the formula: $n = \frac{z^2 p q}{e^2}$, where: 95% confidence level ($z = 1.96$), $p = 0.975$, $q = 0.025$, with a margin of error of 5% ($e = 0.05$), obtaining 38 patients per group for the sample.

12. Framework

Item 12: Superiority, equivalence or non-inferiority trial hypothesis testing framework, and wick comparisons will be presented on this basis.

The effect of NSS in increasing survival and reducing mortality in patients with COVID-19 will be demonstrated by the significant superiority of IG over CG.

13. Statistical Interim analyses and stopping guidance

Item 13a: Information on interim analyses specifying what interim analyses will be carried out and listing of time points:

No interim analyses are planned in the study.

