- SpO2 without supplemental oxygen, use of home oxygen upon hospital discharge, days of supplemental oxygen use, post-covid syndrome, decrease in body weight: all will be analyzed from hospital discharge until day 40.

Section 4: Statistical Principles

16. Confidence intervals and p-values

Item 16: Level of statistical significance

P values ≤ 0.05 will be considered indicative of statistical significance in all cases. P values will be one-sided.

Item 17: Description of any planned adjustment for multiplicity, and if so, including how the type I error is to be controlled

This study will not analyze data that required multiplicity tests. To avoid type 1 error, an alpha value of 5% will be used (considering $p < 0.05$ significant), aberrant data will be eliminated, validated tests applicable to the study variables will be defined and established, specific inclusion criteria will be implemented for homogenization of the sample to avoid bias variables, and a specific sample size calculation will be performed.

Item 18: Confidence intervals (CI) to be reported

All the confidence intervals presented will be 95%.

19. Adherence and Protocol Deviations

Item 19a: Definition of adherence to the intervention and how this is assessed including extent of exposure.

The intervention will consist of: 1) 2 envelopes of NSS taken in a period of less than 15 minutes (without the presence of vomiting) after morning and afternoon meals during the first 21 days or until hospital discharge, 2) 1 capsule of *Saccharomyces Boulardii* before the NSS and 1 capsule with the second envelope for 6 days or until hospital discharge, 3) intramuscular B complex; 1 ampoule after meals for 5 days or at hospital discharge.

Adherence to treatment will be established as taking more than 95% of the NSS and not fasting for 2 consecutive days.

Item 19b: Description of how adherence to the intervention will be presented

The intervention will be applied by the research team, who will be responsible for the application and collection of data, which will be reported in daily formats in the morning and afternoon shifts.

The clinical investigators are going to prepare each supplement, administer, and witness each intake of the NSS, registering the time as well as any immediate side effects such as vomiting, bloating, and abdominal pain.

Item 19c: Definition of protocol deviation for the trial:

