- Procalcitonin (ng / mL)

27. Analysis methods

To consider statistical significance in the results, a value of $p < 0.05$ will be used.

The analysis of the primary and secondary outcomes is shown in the following table.

Variable	Outcome	Timing	Normality test	Summary results	Parametric test	Nonparametric test	Categorical data test	Analysis type
Overall survival	Primary	40 days follow-up	-	Kaplan-Meier	-	-	Log Rank	Intergruppal
Progression to intubation	Primary	until the last patient is intubated	-	Kaplan-Meier	-	-	Log Rank	Intergruppal
Survival in intubated	Primary	40 days follow-up	-	Kaplan-Meier	-	-	Log Rank	Intergruppal
Oxygen flow (L)	Secondary	Basal vs day 3	Shapiro-Wilk	Mean and SD	Paired T test	Wilcoxon	-	Intragruppal
qSOFA (pts)	Secondary	Basal vs day 3	Shapiro-Wilk	Mean and SD	Paired T test	Wilcoxon	-	Intragruppal
Defecations per day (No.)	Secondary	Day 3	Shapiro-Wilk	Mean and SD	Unpaired T test	Mann Whitney	-	Intergruppal
Distension (Yes/No)	Secondary	Day 3	Shapiro-Wilk	Proportions	-	-	Fisher	Intergruppal
PHQ-9 (pts)	Secondary	Basal vs Discharge	Shapiro-Wilk	Mean and SD	Paired T test	Wilcoxon	-	Intragruppal
Oxygen saturation >90%	Secondary	Day 3	Shapiro-Wilk	Proportion	-	-	Fisher	Intergruppal
Hydric balance	Secondary	Day 3	Shapiro-Wilk	Mean and SD	Unpaired T test	Mann Whitney	-	Intergruppal
Bristol scale "normal"	Secondary	Day 3	Shapiro-Wilk	Proportion	-	-	Fisher	Intergruppal
Saturation without supplemental O2	Secondary	Day 40	Shapiro-Wilk	Mean and SD	Unpaired T test	Mann Whitney	-	Intergruppal
Need for supplemental O2 at home	Secondary	Day 40	Shapiro-Wilk	Proportion	-	-	Fisher	Intergruppal
Days of supplemental O2 use at home	Secondary	Day 40	Shapiro-Wilk	Mean and SD	Unpaired T test	Mann Whitney	-	Intergruppal
Postcovid syndrome	Secondary	Day 40	Shapiro-Wilk	Proportion	-	-	Fisher	Intergruppal
Decrease in weight	Secondary	Day 40	Shapiro-Wilk	Proportion	-	-	Fisher	Intergruppal
Gastrointestinal symptoms	Secondary	Day 40	Shapiro-Wilk	Proportion	-	-	Fisher	Intergruppal

28. Missing data

Item 28: Missing data-reporting and assumptions/statistical methods to handle missing data

(multiple imputation)

Statistical methods to handle missing data will not be performed.

30. Harms

Item 30: Sufficient detail provided on summarizing harms

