D dimer – ng/mL	291.2 ± 179.9	444.9 ± 954.9	0.927
Creatinine – mg/dL	0.88 ± 0.31	0.86 ± 0.22	0.734
Urea – mg/dL	33.95 ± 15.84	32.95 ± 10.78	0.710
BUN – mg/dL	15.87 ± 7.39	15.43 ± 5.02	0.690
GFR – mL/min/1.73 m ²	90.15 ± 20.2	93.59 ± 17.4	0.673
Procalcitonin – ng/mL	0.364 ± 0.6	0.18 ± 0.188	0.356

The comparison of both groups in the baseline did not show a significant difference in any item analyzed in this study.

SD, Standard Deviation. CG, control group. IG, intervention group. MNA, Mini Nutritional Assessment.

Figure 2. Kaplan-Meier general survival curve from CG and IG patients

[figure not shown]

Figure 2. Kaplan-Meier general survival curve from CG and IG patients.

The proportion of patients in the IG (blue line) and the CG (red line) included in the study and completed a 40-day follow-up from September 2020 to April 2021. The cumulative proportion of surviving patients was estimated with the Kaplan-Meier method and compared in both groups, from the CG died seven of 40 patients (surveillance 82.5%, mean 36.22, 95% of confidence interval [CI] 33.46 to 38.98), otherwise from de IG died one of 40 patients (surveillance 97.5%, mean 39.31%, 95% of [CI], 37.98 to 40.64). This showed a significant difference of IG compared to CG * $p=0.027$ (Log Rank test, 95% of [CI]).

Figure 3. Kaplan-Meier survival curve from patients Receiving Mechanical Ventilation of the CG and IG.

Figure 3-A

[figure not shown]

Figure 3-B

[figure not shown]

Figure 3. Kaplan-Meier survival curve from patients Receiving Mechanical Ventilation of the CG and IG.

The proportion of patients with MVA from CG and the IG were included in the study and completed 40-day follow-up from September 2020 to April 2021. **(Figure 3-A)** IG and CG were analyzed with the Kaplan-Meier method comparing both groups to MVA progression, from CG seven patients progressed to MVA (17.5%, mean 9.68%, [IC] of 95%, 8.66 to 9.80); meanwhile, from IG three patients progressed to MVA (7.5%, mean 9.68%, [IC] of 95%, 9.34 to 10.03), this represents a 10% decrease in MVA progression of IG in comparison with CG. **(Figure 3-B)** In overall survival and mortality with MVA, five out of seven patients died in CG (71.4%, mean 19.42, [CI] of 95%, 13.09 to 25.76). One out of three patients died in IG (33.5%, mean 26.66, [IC] of 95% 11.73 to 41.6), this represents the 38.1% decrease in mortality with MVA in IG compared to CG.

Table 2-A. Clinical evolution and 40-day follow up.

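### The primary survival comparison has no between-arm estimate with an interval, and the per-arm mean intervals printed instead run past the outcome's 40-day limit

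*SAP*

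**What the plan says.** - **Method.** The SAP Item 27 row for "Overall survival" reads "Kaplan-Meier - - Log Rank Intergruppal". It names no hazard ratio, risk difference or difference in mean survival, and does not say whether the log-rank p is large-sample or exact.
- **Decision rule.** Item 12 says the effect "will be demonstrated by the significant superiority of IG over CG". Item 27 sets the threshold: "To consider statistical significance in the results, a value of $p < 0.05$ will be used". Item 16 adds: "P values will be one-sided".
- **Intervals.** Item 18 says only "All the confidence intervals presented will be 95" per cent. It does not say of which quantity or by which method.
- **Horizon.** Items 14, 15 and 26a run overall survival from baseline to day 40 or death. Item 14 also puts each patient's last study day 40 days after discharge.
- **What is printed.** Figure 2 gives 7 of 40 control (CG) deaths, mean 36.22 (33.46 to 38.98), and 1 of 40 IG deaths, mean 39.31 with interval "37.98 to 40.64". It concludes: "This showed a significant difference of IG compared to CG", p=0.027. Figure 3-B gives 1 death among 3 intubated IG patients, mean 26.66 (11.73 to 41.6).

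**The concern.** The claim of superiority rests on one p-value from eight deaths split 7 to 1. A p-value does not show how large or how uncertain an effect is, and the only intervals offered describe each arm separately. One of those for overall survival includes values that cannot occur, so it misstates the uncertainty in the arm with the fewest events. A large-sample log-rank p also deserves a check at eight deaths. At stake is how firmly a reader may take the main mortality claim, and whether the SAP shows the imprecision that goes with it.

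**Working it through.** **Inputs.** 40 per arm; deaths 7 (CG) and 1 (IG); printed means, intervals and p from Figures 2 and 3-B. Death days are not printed. I assume no censoring before day 40, which fits the printed survival: 33/40 = 82.5% and 39/40 = 97.5%.

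**1. Reproduce the IG mean interval.** With one death at day t, mean = 40 − (40 − t)/40. Setting this to 39.31 gives 40 − t = 27.6, so t = 12.4.
- SE = 27.6 × √(1/40 × 39/40) / √40 = 0.681.
- 39.31 ± 1.96 × 0.681 = 37.97 to 40.65, against 37.98 to 40.64 printed.

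So the interval is normal-theory with a 40-day horizon. Its upper limit is 40 + (40 − t)/40 × (1.96 × √(39/40) − 1) = 40 + 0.935 × (40 − t)/40. With a single death this exceeds 40 whatever the day of death before day 40.

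**2. Intubated IG patients (a separate outcome, n = 3).** A death at day 8 with a 36-day horizon, both chosen to fit, gives mean 36 − 28/3 = 26.67 and SE = 28 × √(1/3 × 2/3) / √3 = 7.62. The interval is 11.73 to 41.60, which matches the print.

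**3. The missing effect estimate.** Risk difference = 0.175 − 0.025 = 0.150. The Wilson limits are [p + z²/2n ± z√(p(1−p)/n + z²/4n²)] / (1 + z²/n):
- CG deaths: 0.0875 to 0.3195.
- IG deaths: 0.0044 to 0.1288.

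Newcombe limits:
- Lower: 0.150 − √[(0.175 − 0.0875)² + (0.1288 − 0.025)²] = 0.014.
- Upper: 0.150 + √[(0.3195 − 0.175)² + (0.025 − 0.0044)²] = 0.296.

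The effect is therefore 15.0 points, 95% CI 1.4 to 29.6. The same Wilson limits give day-40 survival of 68.1% to 91.3% (CG) and 87.1% to 99.6% (IG), all within range.

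**4. Reproduce the p-value.** Log-rank for untied deaths, by position of the IG death among the eight:

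| IG death | O − E (CG) | V | z | two-sided p | one-sided p |
|---|---|---|---|---|---|
| 3rd | 3.120 | 1.997 | 2.208 | 0.0273 | 0.0136 |
| 4th | 3.133 | 1.997 | 2.217 | 0.0266 | 0.0133 |

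Only these two positions round to 0.027. One-sided p lies between 0.012 and 0.014 for all eight positions, so the printed value is two-sided.

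**5. Exact version of the same test.** Under permutation of arm labels:
- All eight deaths in CG: C(72,32)/C(80,40) = 0.002653.
- Each particular order of seven CG deaths and one IG death: C(72,33)/C(80,40) = 0.003216.

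As extreme or more so are the 8–0 pattern and every 7–1 order with the IG death at the observed position or later:
- 3rd: 0.002653 + 6 × 0.003216 = 0.0219 one-sided, 0.044 two-sided.
- 4th: 0.002653 + 5 × 0.003216 = 0.0187 one-sided, 0.038 two-sided.

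The ratio to the printed-type p is 0.0439/0.0273 = 1.6 or 0.0375/0.0266 = 1.4. Sets of death days built to fit the printed CG mean and interval and p=0.027, with ties allowed, gave exact two-sided p from 0.037 to 0.057 (median 0.044). About 18% of these sets exceeded 0.05; that is a share of constructed sets, not a probability.

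**6. True size given eight deaths.** The large-sample test rejects for the 8–0 and all 7–1 patterns: 0.002653 + 8 × 0.003216 = 0.0284 in one direction. The two-sided 5% test therefore has size 5.7%, and the one-sided 5% test 2.8%.

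**The case against.** **The verdict does not turn on this.** That largely stands. Without ties the exact log-rank stays below 0.05. Barnard and Boschloo tests both give 0.033, and the Newcombe interval excludes zero. Under Item 16's one-sided rule the exact p is about 0.02, and the one-sided 5% test is conservative.

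A reader might go further and infer that the mortality result is really non-significant, citing two-sided Fisher (0.057) or a hazard-ratio Wald interval of 0.016 to 1.09. The documents do not support that. Fisher ignores the timing of deaths, and the profile-likelihood interval for the same hazard ratio (0.007 to 0.76) excludes 1. This disagreement is a reason to name the interval method in advance, not evidence of no effect.

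**The plan did not ask for the faulty intervals.** Correct. Neither Item 27 nor Item 18 prescribes intervals for mean survival; they appear only in the figure legends. Item 27's fault is that it leaves the effect measure and interval method open.

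**The effect size is visible.** Also correct: 82.5% and 97.5% are printed, so a reader can subtract. What is missing is the interval.

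**The horizon might be longer than 40 days.** Item 14's after-discharge wording allows the thought, but the overall-survival outcome is defined to day 40 and the printed mean and interval reproduce with 40.

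**The replacement limits are approximations too.** True of Wilson and log-log limits with one event, but they cannot leave the possible range. For IG survival, Wilson (87.1% to 99.6%) is close to the exact binomial interval (86.8% to 99.9%).

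**Conclusion.** The point holds on two counts that need no assumption about the order of deaths. No between-arm estimate with an interval is planned or printed for overall survival, and the printed IG mean-survival limit is 0.64 days above the largest possible value. The 41.6 limit shows the same fault in the separate intubated-patient outcome, and is not further evidence about overall survival.

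The main quantity missing is the interval from 1.4 to 29.6 points. It runs from a very small benefit to a very large one.

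The p-value is a lesser matter. It is too small by a factor of about 1.4 to 1.6 if deaths are untied and nobody was censored early, and its two-sidedness conflicts with Item 16. The conclusion at 0.05 most likely survives. Certainty would need the actual death days, because some tied patterns push the exact two-sided p just above 0.05.

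**What to change.** 1. In Item 27 and Figure 2, add one between-arm estimate for overall survival: the day-40 risk difference with a Newcombe (score) 95% CI. Label it post hoc, because the SAP already contains the results.
2. In the figure legends, replace the intervals for mean survival with day-40 survival per arm and limits that stay within 0 to 100% (Wilson or log-log).
3. Keep the log-rank as the stated test and print a permutation log-rank p beside it, computed from the actual death days.
4. State whether the printed p is one- or two-sided, and reconcile it with Item 16.

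A penalised hazard ratio with profile limits is optional. No new data are needed. The cost is a little analysis work, a visibly wide interval and a slightly larger p-value.

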Item 13b: Any planned adjustment of the significance level due to interim analysis:

No adjustment of the significant level due to interim analysis are planned.

13c. Details of guidelines for stopping a trial early:

The following points are considered in planning the early stopping of the study:

1. That the intervention causes serious adverse effects in patients generating insecurity in its application.
2. That the investigators detect improbable, ineffective, or extreme differences between the CG and the IG.

3. New information emerges that raises serious safety issues or convincingly answers to the main question.

14. Timing of final analysis

Item 14: Timing of final analysis e.g all outcome analyzed collectively or timing stratified by planned length of follow-up

The follow-up will start in September 2020 until the established sample is met.

The last day of the study for each patient is going to be 40 days after hospital discharge.

Statistical analysis of clinical and biochemical variables will be performed on baseline, day three, hospital discharge and day 40. Analysis of overall survival and mortality will be performed from baseline to day 40 or patient death. Progression of patients to Mechanical Ventilation Assistance (MVA) will be performed from baseline until the last patient is intubated, mortality in patients with MVA will be performed from intubation to day 40 or death.

15. Timing of outcome assessments

Item 15: Time points at which the outcomes are measured

Survival and Mortality

- Overall survival and mortality: performed from baseline to day 40 or patient death.
- Progression of patients to Mechanical Ventilation Assistance (MVA): performed from baseline until the last patient is intubated.
- Mortality in patients with MVA: performed from intubation to day 40 or death.

Clinical and biochemical variables

- Delivered oxygen flow and maintenance of SpO₂ > 90%: will be analyzed at baseline and day three.
- qSOFA scale: will be analyzed at baseline compared with day three.

- Gastrointestinal function (average of gastrointestinal movements, abdominal distension, and Bristol scale): will be analyzed at baseline compared with day three.
- Laboratory parameters: will be analyzed at baseline, day three and hospital discharge.
- PHQ-9: will be analyzed at baseline and hospital discharge.

Follow-up at day 40

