Categorical data will be summarized by numbers and percentages. Normality tests will be applied to evaluate the distribution of the data. If the continuous data present a normal distribution, they will be assumed by mean, SD, and range. If they do not present a normal distribution, they will be summarized with the median and the IQR. Minimum and maximum values will also be presented for continuous data. Statistical significance tests will be performed between both groups in the baseline to rule out significant differences.

Section 6: Analysis

26. Outcomes definitions

Item 26a: Specification of outcomes and timings

Primary outcomes

- Overall mortality and survival will be assessed from the baseline to day 40.
- Progression to AVM will be assessed from baseline until the last patient is intubated.
- Mortality and survival in intubated patients will be assessed from baseline to day 40.

These results will be included in the results section of the manuscript.

Secondary Outcomes

Administration of supplemental oxygen flow, oxygen saturation (spO₂), qSOFA scale, and gastrointestinal function will be assessed by comparing at baseline to day 3 intragroup and intergroup. The PHQ-9 test will be assessed at baseline and at discharge between both groups.

These results will be included in the secondary outcomes section of the manuscript. Analysis of the association of baseline biochemical parameters and mortality will be considered in a table and in the secondary outcomes section of the manuscript.

The spO₂ without supplemental oxygen requirement, home supplemental oxygen requirement, post COVID syndrome, and body weight at day 40 will be analyzed between both groups in a table.

These results are included in the follow-up section of the manuscript.

Item 26b: Specific measurement and units

- SpO₂ (%)
- Mortality (days of death)
- Kilocalories (kcal / day)
- PHQ9 (pts).
- Temperature (°C).
- Hemoglobin (g / dL).
- Mean corpuscular volume (fL).
- Mean corpuscular hemoglobin concentration (g / dL).
- Leukocytes ($10^3 / \mu\text{L}$).
- Neutrophils (%).
- Platelets ($10^3 / \mu\text{L}$).
- Glucose (mg / dL).
- Total cholesterol (mg / dL).
- Triglycerides (mg / dL).
- Aspartate aminotransferase (U / L).
- Alanine aminotransferase (U / L).
- Albumin (g/dL).
- Blood Urea Nitrogen (mg / dL).
- Urea (mg / dL).
- Creatinine (mg / dL).
- Glomerular filtration rate
- Ferritin (ng / mL)
- Fibrinogen (mg / dL)
- C-reactive protein (mg / L)
- Dimer-D (ng / mL)

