Risk factors and coexisting conditions – (%)			
Overweight	38 (95%)	36 (90%)	0.338
Obesity	14 (35%)	13 (32.5%)	1
DM 2	13 ± 0.325	11 ± 0.275	0.404
Cardiovascular disease	17 (42.5%)	10 (25%)	0.078
Hyperlipidemia	11 (27.5%)	7 (17.5%)	0.422
Gastrointestinal Disease	14 (35%)	13 (32.5%)	1
Total Risk Factors	2.92 ± 1.42	2.57 ± 1.35	0.261
Covid-19 Symptoms			
Dyspnea	24 (60%)	26 (65%)	0.409
Nausea and vomit	6 (15%)	7 (17.5%)	0.5
Hyposmia	12 (30%)	15 (37.5%)	0.637
Dysgeusia	18 (45%)	20 (50%)	0.412
Headache	26 (65%)	29 (72.5%)	0.315
Myalgia	32 (80%)	30 (75%)	0.395
Diarrhea	18 (45%)	12 (30%)	0.124
Anorexia	20 (50%)	21 (52.5%)	0.500
Total of symptoms	7.05 ± 2.11	6.8 ± 2.23	0.608
Gastrointestinal Clinic			
Bristol	9 (50%)	5 (27.8%)	0.153
Number of defecations	0.54 ± 0.6	0.52 ± 0.73	0.717
Abdominal distension	28 (70%)	28 (70%)	0.596
Vital Signs			
Breathing Frequency - bpm	21.18 ± 3.01	21.48 ± 3.01	0.378
Oxygen Saturation - %	92.73 ± 4.17	94 ± 3.18	0.144
Heart Rate - bpm	70.7 ± 15.4	75.5 ± 9.88	0.105
Temperature – °C	36.27 ± 0.73	36.3 ± 0.62	0.935
Oxygen flow – L/min	5.9 ± 3.82	6 ± 3.29	0.571
qSOFA - pts	0.425 ± 0.59	0.65 ± 0.62	0.100

SD, Standard Deviation. CG, control group. IG, intervention group.

Table 1-B. Clinical characteristics and baseline parameters of CG and IG.

Characteristics	CG	IG	P - value
	Mean (SD / %) n = 40	Mean (SD / %) n = 40	
Nutritional Status			
MNA® - pts	11.13 ± 2.26	11.38 ± 1.65	0.828
BMI – kg/m ²	29.35 ± 3.89	29.98 ± 4.07	0.403
Hydric balance – mL/day	-203.4 ± 966	-301.5 ± 1167	0.806
Medication			
Antihypertensive	13 (32.5%)	9 (22.5%)	0.227
Antidiabetics	9 (22.5%)	11 (27.5%)	0.398
Antilipids	3 (7.5%)	3 (7.50%)	0.662
Antibiotics	1 (2.50%)	4 (10%)	0.359
Antiacids	6 (15%)	6 (15%)	0.662
NSAIDs	8 (20%)	12 (30%)	0.220
Laboratory studies			
Hb – g/dL	15.53 ± 2.222	15.54 ± 2.088	0.987
MCHC – g/dL	33.39 ± 1.4	33.46 ± 1.17	0.753
Platelets – 10 ³ /μL	222.2 ± 53.93	248.4 ± 139.9	0.790
Leukocytes - 10 ³ /μL	8.97 ± 4.15	8.46 ± 4.36	0.400
Neutrophils - %	83.5 ± 8.87	80.78 ± 9.29	0.172
Glycemia – mg/dL	135.4 ± 59.39	134.8 ± 58.83	0.872
Total cholesterol – mg/dL	142.8 ± 42.82	135 ± 23.53	0.335
Triglycerides – mg/dL	147.5 ± 58.92	132.8 ± 37.39	0.533
AST – U/L	48.06 ± 28.81	46.4 ± 49.65	0.214
ALT – U/L	47.69 ± 31.9	50.44 ± 50.88	0.914
Albumin – g/dL	3.53 ± 0.44	3.57 ± 0.41	0.768
Ferritin – ng/mL	1070 ± 899.3	1270 ± 1142	0.572
Fibrinogen – mg/dL	592.2 ± 170.4	607.4 ± 162.9	0.721
CRP – mg/dL	157.3 ± 106.7	135.3 ± 94.92	0.313

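### SAP Item 27 compares day-3 defecations, hydric balance, distension and saturation between arms without their collected baselines; this costs precision and, for saturation and gastrointestinal function, does not match Item 26a

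*SAP*

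**What the plan says.** Item 27 introduces its table with "The analysis of the primary and secondary outcomes is shown in the following table". In that table:

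- The row beginning "Defecations per day (No" and the hydric balance row have timing day 3 and an unpaired t-test or Mann-Whitney test between groups.
- Distension, saturation above 90% and normal Bristol have timing day 3 and a Fisher test between groups.
- Decrease in weight is a day-40 proportion with a Fisher test.
- No row has a covariate.

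Two earlier items describe something different. Item 15 says of gastrointestinal function (bowel movements, "abdominal distension, and Bristol scale): will be analyzed at baseline compared with day three"), and lists saturation above 90% at both baseline and day three. Item 26a says that oxygen flow, saturation, qSOFA and gastrointestinal function "will be assessed by comparing at baseline to day 3 intragroup and intergroup". Hydric balance appears in neither item. For weight, Item 26a names body weight at day 40, and Item 15 places weight decrease in the period from discharge to day 40.

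The baselines exist. Table 1-A has "Number of defecations", Bristol, distension and saturation, and Table 1-B has hydric balance. The protocol (Procedure) records weight before assignment and every two days in hospital.

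**The concern.** A baseline measurement of the same quantity usually predicts the follow-up value. Putting it in the between-arm model removes that part of the patient-to-patient variation and corrects the estimate for any chance difference at the start. With about 40 patients per arm, and fewer for several rows, that gain is worth having and needs no new data.

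Item 25b instead relies on significance tests at baseline. A non-significant baseline p-value neither recovers the lost precision nor removes an imbalance that is present.

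There is also a consistency problem. For saturation and gastrointestinal function, a reader of Item 26a expects a between-group comparison that uses baseline, and Item 27 does not supply one. If the mismatch stays, the choice between the two is open after the results are known.

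**Working it through.** **The plan's own figures.** The sample size reproduces: 1.96² × 0.975 × 0.025 / 0.05² = 37.46, rounded up to 38. It is a precision formula for one proportion, with no SD, effect or power, so it sets no target for these outcomes. The Table 2-A p-values also reproduce from day-3 summaries alone:

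| Outcome | Input (control v intervention) | Recomputed p | Stated p |
|---|---|---|---|
| Defecations | 0.81 ± 0.90 (n=37) v 1.41 ± 1.13 (n=36) | 0.014 | 0.014 |
| Hydric balance, mL | 123.4 ± 453.8 (n=17) v 456.6 ± 485.5 (n=18) | 0.044 | 0.043 |
| Distension | 16/31 v 6/31 | 0.008 | 0.008 |
| Saturation >90% | 34/40 v 37/40 | 0.241 | 0.241 |
| Bristol | 8/24 v 13/31 | 0.356 | 0.356 |

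So the reported tests are the unadjusted ones. (The t-tests match two-sided values and the Fisher tests one-sided values, while Item 16 says "P values will be one-sided". That is a separate point.)

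**Precision, linear models only.** The baseline-to-day-3 correlation ρ is not in the documents, so 0.3 to 0.7 is assumed. ANCOVA multiplies the variance by 1 − ρ². For defecations, the unadjusted SE = √(0.90²/37 + 1.13²/36) = 0.2395, and the half-width is 1.99 × 0.2395 × √(1 − ρ²).

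| ρ | 1 − ρ² | Variance falls by | 40 per arm acts like | Defecation half-width |
|---|---|---|---|---|
| 0 | 1 | 0 | 40 | 0.48 |
| 0.3 | 0.91 | 9% | 44 | 0.45 |
| 0.5 | 0.75 | 25% | 53 | 0.41 |
| 0.7 | 0.51 | 49% | 78 | 0.34 |

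For hydric balance (pooled day-3 SD 470, about 17.5 per arm), the difference detectable with 80% power at one-sided 0.05 is (1.645 + 0.842) × 470 × √(2/17.5) = 395 mL. It falls to 377, 342 or 282 mL at the three values of ρ.

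**Chance imbalance at baseline.**

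- *Saturation:* 92.73 ± 4.17 v 94 ± 3.18, a gap of 1.27 or 0.34 SD (pooled SD 3.71). If values were normal, about 74% v 90% were already above 90% at baseline. That is a wider gap than the 85% v 92.5% tested on day 3.
- *Hydric balance:* −203.4 v −301.5, a gap of 98.1/1071 = 0.09 SD. Adjustment moves the estimate by ρ × (470/1071) × 98.1, from 333 mL to 346, 355 or 363 mL.
- *Defecations:* 0.54 v 0.52. The estimate moves only from 0.60 to about 0.61 to 0.62.
- *Distension:* 28/40 in each arm, so no imbalance.

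**Why ANCOVA and not a change score.** The baseline SD of hydric balance (966 and 1167) is about twice the day-3 SD. Even at ρ = 0.7 the SD of the change is √(470² + 1071² − 2 × 0.7 × 470 × 1071) = 814, well above 470.

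**Bristol.** Baseline counts of 9 (50%) and 5 (27.8%) imply about 18 patients per arm, against 24 and 31 on day 3. A complete-case adjusted model keeps at most 18 + 18. On the linear formula, breaking even needs 1 − ρ² = (1/24 + 1/31)/(1/18 + 1/18) = 0.665, so ρ of about 0.58.

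**Weight.** Under normality, a yes/no cut keeps φ(c)²/[p(1 − p)] of the information in the continuous change: about 63% at p = 44.4% and 56% at p = 72.7%, the proportions in Table 2-A (18 and 11 patients).

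**The case against.** The strongest reply is that nothing here is wrong. Comparing randomised arms on day 3 is valid without baseline adjustment, and all these outcomes are secondary. That stands. A reader might infer from the mismatch that the reported day-3 tests are biased or invalid; the documents do not support that.

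Three further limits also stand.

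- The contradiction is narrow. Only Item 26a promises a between-group comparison; Item 15 does not say between whom. Hydric balance is in neither item, so there the argument is efficiency alone.
- The 1 − ρ² factor belongs to linear models. It cannot be carried over to distension, saturation above 90% or Bristol. Logistic adjustment targets a conditional odds ratio, usually with a larger standard error.
- Adjusting everything could do harm. Bristol would lose patients. Saturation above 90% has only 6 + 3 = 9 patients below the cut, which is thin for an adjusted logistic model.

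On weight, one might say that the plan throws the earlier value away. It does not: a decrease already needs an earlier weight. What is lost is the size of the change, and which earlier weight counts is not stated.

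The reply does not dispose of the missing Item 26a analysis, of the precision available for the continuous outcomes, or of the saturation gap.

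**Conclusion.** The point holds as a loss of precision on secondary outcomes, together with an inconsistency between Items 26a and 27 for saturation and gastrointestinal function. The gain from adjustment in linear models is 9% to 49% of the variance, on the assumption that ρ lies between 0.3 and 0.7. At the low end it is small (defecation half-width 0.48 to 0.45). Chance imbalance matters visibly only for saturation among the outcomes to be adjusted, and the 74% v 90% figure rests on normality. Defecations, distension and hydric balance were close to balanced, so adjustment there would sharpen the estimates and barely move them. It should be changed, but it does not undermine the trial's primary comparison.

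**What to change.** 1. Reconcile Items 15, 26a and 27, so that each outcome has one stated between-arm analysis.
2. For defecations, hydric balance and saturation as a continuous percentage, use ANCOVA: day-3 value on arm and baseline value. Keep saturation above 90% as description.
3. For distension, use Mantel-Haenszel stratified by baseline distension.
4. Leave Bristol unadjusted, or adjust it only as a sensitivity analysis.
5. Analyse day-40 weight in kg, adjusted for one reference weight, and state whether that is baseline or discharge. Keep the yes/no figure as description.

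The cost is SAP wording and a few models in SPSS, which Item 31 already names. Two downsides need stating. Patients without a baseline value drop out of the adjusted models, because Item 28 uses no missing-data method, so the number analysed should be shown beside each estimate. And since the SAP already contains results, the adjusted analyses must be labelled as added after the data were seen and reported beside the unadjusted ones.
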